14.3 Statistical analysis plan

Primary Outcome:

- Pathologic complete response: the proportion of the 48 patients having a pathologic complete response with a 95% confidence interval (using normal approximation) will be calculated.

Secondary Outcomes:

- *Safety:* Adverse events of grades 3, 4, 5 by the CTCAE v4.3 criteria for each category listed in section 2.1.6 will be summarized. The proportion of patients with each category of AE will be calculated with a 95% confidence interval. After the enrollment of the first 20 patients, we will evaluate the rate of surgical resection. If >6 patients are not able to proceed with surgery due to excessive toxicity or progression (not including occult metastatic peritoneal disease that was found during surgery and not on imaging) the study will discontinue due to unacceptable toxicity.

- *Ability of patients to undergo surgical resection after receiving neoadjuvant FOLFIRINOX*: the proportion of patients who are able to go through surgery among those who have resectable tumor will be calculated accompanied with a 95% confidence interval.
- *Rate of resectability* will be evaluated by determining the proportion of patients who are able to undergo surgery with resection of their primary tumor (R0 vs R1) resection. A 95% confidence interval will be constructed for the rate.
- *Disease free survival (DFS)*: DFS is defined as time from registration to evidence of tumor recurrence (including clinical deterioration related to the underlying pancreatic cancer, as assessed by the investigator) or death from any cause. Kaplan-Meier curve for DFS will be plotted. Median DFS time will be calculated accompanied with a 95% confidence interval.
- *Overall survival*: time from registration to death for 48 patients with right censoring will be analyzed using Kaplan-Meier estimate. Median survival time will be obtained accompanied with a 95% confidence interval.
- *Objective response rate*: proportion of patients with complete responses (CR) or partial responses (PR) after 4 cycles of FOLFIRINOX treatment will be constructed with a 95% confidence interval.
- *Disease control rate*: Proportion of patients with complete responses (CR), partial responses (PR), or stable disease (SD) after 4 cycles of FOLFIRINOX treatment will be obtained with a 95% confidence interval.

Tertiary Outcomes:

- Quality of life measures (from PG-SGA and FAACT) will be summarized with descriptive statistics and compared between baseline and 4 weeks post neo-adjuvant therapy with paired t-tests.

Correlative Outcomes:

- Change of biomarkers (including Ca19-9 and other tissue markers) from baseline to after 2 cycles of therapy will be calculated. Paired t-test will be used to test the change. We will correlate the change of Ca19-9 with patients' pathologic complete response using logistic regression model or overall survival using Cox proportional hazards model as appropriate. Biomarkers will also be correlated with PFS and other response outcomes similarly.
- Differential expression will be performed in R using DESeq2. These files will be downloaded and uploaded to Partek Genomics Suite v6.6 for visualization. Pathway analysis will be performed using Ingenuity Pathway Analysis. CIBERSORT analysis to identify the immune cell make up based on gene expression will also be performed. Selected differentially expressed markers will be correlated with outcomes as describe above.

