14. STATISTICAL METHODS

14.1 Sample size analysis and accrual

The pathological complete response with traditional chemotherapy in pancreatic cancer is very low (no reported complete response in neoadjuvant studies). We aim to evaluate the complete response rate and the correlation with outcome. So we assume the pathological complete response in traditional chemotherapy to be 1%. We expect that the pathological complete response after 2 cycles of FOLFIRINOX therapy is about 10%. We plan to enroll 48 patients over a 24 months period. Assuming 90% of patients are evaluable for response, we will have 43 patients evaluable for pathological complete response. Patients will be considered non-evaluable and be replaced with new subjects per analysis datasets section below. With evaluable patients, we have 82% power detect a significant difference from the traditional chemotherapy with a 5% Type I error rate using a two sided one-sample test for proportion.

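### The primary pCR analysis in Section 14.3 uses a normal-approximation interval that is unsuitable for the 4 to 5 events expected, and it does not carry over the test on which Section 14.1 sizes the trial

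*Combined protocol and SAP*

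**What the plan says.** Section 14.1 takes a pCR rate of 1% for traditional chemotherapy and expects about 10% after two cycles of FOLFIRINOX. On numbers it says "We plan to enroll 48 patients over a 24 months period" and "Assuming 90% of patients are evaluable for response, we will have 43 patients evaluable for pathological complete response". It then claims that "we have 82% power detect a significant difference from the traditional chemotherapy". The basis given for this figure is "a 5% Type I error rate using a two sided one-sample test for proportion". It does not say which version of that test was used.

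Section 14.3 gives the primary analysis in one line: "the proportion of the 48 patients having a pathologic complete response with a 95% confidence interval (using normal approximation) will be calculated". That line contains no hypothesis test, no 1% reference value, no critical number of responses and no success criterion. No other section supplies them.

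**The concern.** A normal approximation to a binomial proportion needs more events than this trial expects. With 4 to 5 pCRs the sampling distribution is clearly skewed, so a symmetric interval is placed too low and its upper limit is too small. With fewer pCRs the limits become impossible or the interval collapses. Section 14.1 itself notes that neoadjuvant studies have reported no complete response, so counts of 0 to 3 are realistic.

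The second difficulty is that design and analysis do not connect. The sample size rests on a test against 1%, but the analysis section promises only an interval. A reader of Section 14.3 would judge the result by whether the interval excludes 1%. At some likely counts that gives a different answer from the test that justified the sample size. The version of the test and the rejection count also remain open until after the data are seen.

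**Working it through.** **Inputs.** From Section 14.1: null rate 1%, expected rate 10%, two-sided 5%, 48 enrolled, 43 evaluable (0.90 × 48 = 43.2). From Section 14.3: 48 patients, normal-approximation 95% interval. Because the two sections use different denominators, everything is shown for both.

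**Step 1: the plan's own power.** The exact binomial test at n = 43 gives P(X ≥ 2 | 1%) = 0.069 and P(X ≥ 3 | 1%) = 0.0092, so it rejects at 3 or more. There is no lower rejection region, since P(X = 0 | 1%) = 1 − 0.351 = 0.649. Power is P(X ≥ 3 | 10%) = 0.8176, which reproduces the stated 82%. At n = 48 the same count applies: P(X ≥ 3 | 1%) = 0.0124, power 87.1%.

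Other versions at n = 43:
- The arcsine formula gives 82.8%.
- A continuity-corrected z test also rejects from 3 (z = 1.64 at 2 pCRs, 3.17 at 3), so its exact power is 81.8%.
- The plain score z formula gives 90.6%, which does not match.

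**Step 2: expected events.** 0.10 × 43 = 4.3 and 0.10 × 48 = 4.8, both below the customary minimum of 5.

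**Step 3: the intervals.** Wald: p̂ ± 1.96 √(p̂(1 − p̂)/n). For 2 of 48: 0.0417 ± 1.96 × √(0.0417 × 0.9583/48) = 0.0417 ± 0.0565, which is −1.5% to 9.8%. Clopper-Pearson limits come from beta quantiles. The p-values are for the exact test of 1%.

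| pCRs | Wald, n=48 (%) | Clopper-Pearson, n=48 (%) | p, n=48 | Wald, n=43 (%) | Clopper-Pearson, n=43 (%) | p, n=43 |
|---|---|---|---|---|---|---|
| 0 | 0 to 0 | 0 to 7.4 | 1 | 0 to 0 | 0 to 8.2 | 1 |
| 1 | −2.0 to 6.1 | 0.1 to 11.1 | 0.38 | −2.2 to 6.8 | 0.1 to 12.3 | 0.35 |
| 2 | −1.5 to 9.8 | 0.5 to 14.3 | 0.083 | −1.6 to 10.9 | 0.6 to 15.8 | 0.069 |
| 3 | −0.6 to 13.1 | 1.3 to 17.2 | 0.012 | −0.6 to 14.6 | 1.5 to 19.1 | 0.009 |
| 4 | 0.5 to 16.2 | 2.3 to 20.0 | 0.0014 | 0.6 to 18.0 | 2.6 to 22.1 | 0.0009 |
| 5 | 1.8 to 19.1 | 3.5 to 22.7 | 0.0001 | 2.0 to 21.2 | 3.9 to 25.1 | 0.0001 |

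The Wald lower limit first exceeds 1% at 5 pCRs. The Clopper-Pearson limit does so at 3, where the exact test first rejects.

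**Step 4: coverage of the nominal 95% interval**, summing binomial probabilities over all counts:

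| True rate | Wald, n=48 | Wald, n=43 | Clopper-Pearson, n=48 | Clopper-Pearson, n=43 |
|---|---|---|---|---|
| 10% | 86.4% | 92.9% | 97.5% | 96.5% |
| 5% | 91.2% | 88.5% | 99.1% | 98.1% |
| 1% | 38.3% | 35.1% | 98.8% | 99.1% |

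The Wald error is mostly on one side. At a true 10% and n = 48 the upper limit is below 10% when X ≤ 2, with probability 1 − 0.871 = 12.9%. At n = 43 this needs X ≤ 1, with probability 1 − 0.938 = 6.2%.

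**Step 5: how often this would show** (n = 48 / n = 43).
- Zero-width interval or negative lower limit, P(X ≤ 3): 28% / 36% at a true 10%; 78% / 83% at 5%.
- Interval contains 1% but the exact test rejects, P(X = 3 or 4) at a true 10%: 0.871 − 0.531 = 34% / 0.818 − 0.433 = 39%.
- If the Wald interval were itself the decision rule, which the plan does not say, at least 5 pCRs would be needed and power would be 53% / 43%.

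**The case against.** The strongest reply is that the test is prespecified. Section 14.1 gives null, alternative, level and sidedness, and it belongs to the same Section 14; the test is merely not repeated in 14.3. That is fair as far as it goes. What is absent from the protocol as a whole is the version of the test and the rejection count. What is absent from 14.3 is any link to the test.

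The plan also does not name the Wald interval, and a Wilson interval rests on a normal approximation too, with coverage of 94.7% (n = 48) and 96.5% (n = 43) at a true 10%. Wald is nevertheless the ordinary reading, and wording that leaves the choice open needs correcting in any case.

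Some of the figures look worse than the planned situation. Coverage moves in a saw-tooth: at n = 48 it is 90.1% at a true 8% and 93.4% at 15%. The 35–38% at a true 1% is almost entirely the zero-event case. With 2 pCRs the interval excludes 10% at n = 48 but not at n = 43. Negative limits could simply be shown as zero. These points temper the size of the problem, but under-coverage remains: at n = 43 it falls to 86.2% at a true 8%.

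Finally, the error does not favour the drug. At a true 1% the Wald lower limit exceeds 1% in only about 0.01% of trials, so a false claim of efficacy is not the danger. The danger is an upper limit that is too low and an interval that appears to contradict a positive test. That conflict at 3 or 4 pCRs does not depend on the exact version: the score z test already rejects at 2 (z = 2.41 at n = 43, 2.20 at n = 48).

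**Conclusion.** The concern holds and should be fixed. For a primary endpoint with 4 to 5 expected events, the specified interval covers a true 10% in 86% (n = 48) or 93% (n = 43) of trials, with the shortfall almost wholly at the upper limit. In about a third or more of trials at the planned rate, it would contain 1% although the exact test rejects 1%.

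This rests on two readings: that the normal approximation means the Wald interval, and that the test in 14.1 is the exact binomial, which is inferred from the match to 82%. The design is not invalid and the power statement stands. The difference between 43 and 48 patients is a separate matter that also needs reconciling; this conclusion holds under either.

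**What to change.** In Section 14.3, replace the normal approximation with an exact (Clopper-Pearson) 95% interval. State the primary test there as the two-sided exact binomial test of a 1% pCR rate at the 5% level, rejecting at 3 or more pCRs. The trial statistician should confirm that this is the test behind the 82%. The rejection count is the same at 43 and 48 patients, so interval, test and stated power would then agree. Attained type I error is 0.9% at n = 43 and 1.2% at n = 48.

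A Wilson interval would also avoid zero-width and negative limits. However, it excludes 1% at 2 pCRs (lower limit 1.3% at n = 43, 1.2% at n = 48), where the exact test does not reject (p = 0.069 and 0.083).

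The change is one of wording; sample size and data collection are unaffected. The price is a conservative interval, with coverage of about 96–99% at true rates of 1%, 5% and 10%, and some extra width: for 5 of 48, 3.5% to 22.7% instead of 1.8% to 19.1%.

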2.2 Secondary Objectives

1. To describe the adverse events associated with FOLFIRINOX when administered preoperatively in patients with resectable pancreatic cancer.
2. To estimate the fraction of patients who can successfully undergo surgery after neoadjuvant chemotherapy.
3. To estimate the overall resectability rate, rate of R0 resection, disease free survival (DFS), overall survival (OS), overall response rate (ORR; complete response (CR) + partial response (PR)), and disease control rate (DCR; CR + PR + stable disease (SD)) after administration of FOLFIRINOX in patients with resectable pancreatic cancer.

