7. TREATMENT PLAN

7.1 Treatment Dosage and Administration

Patients on this trial will be treated with neoadjuvant FOLFIRINOX for 2 cycles (1 cycle = 28 days). Patients will receive FOLFIRINOX on an outpatient basis on days 1 and 15 of each cycle. Following neoadjuvant treatment, patients will undergo repeat imaging (CT or MRI) to be reassessed for resectability of the tumor. Further adjuvant treatment will be determined at the treating physician's discretion (i.e. chemoradiotherapy or adjuvant chemotherapy). It is important to note that post-neoadjuvant therapy is determined by the treating physician per their institutional guidelines and standard of care. While this study will collect data regarding disease progression and survival from the post-neoadjuvant period, this protocol does not dictate post-neoadjuvant treatment which may be done at other institutions.

For patients with an R1 resection, any chemoradiotherapy will be included in the 24 weeks of perioperative therapy. Chemoradiotherapy and the timing in which it will be given will be determined at the treating physician's discretion based on margin status and the patient's recovery. Furthermore, patients who receive chemoradiotherapy may also receive adjuvant chemotherapy; however, this will be based on the treating physician's discretion. Recommended radiosensitization will be through 5FU 200 mg/m²/Day continuous infusions M-F of each week or capecitabine 825 mg/m² PO BID M-F for the duration of radiation therapy. Patients who

receive adjuvant therapy will receive treatment based upon treating physician's discretion with a recommended duration of therapy lasting 6 months accounting for preoperative therapy.

The neoadjuvant FOLFIRINOX regimen starting doses are: oxaliplatin 85 mg/m², followed by leucovorin 400 mg/m² given simultaneously with irinotecan 180 mg/m², followed by 5FU 400 mg/m² bolus and then 2400 mg/m² (Table 1). Patients require a PORT, PICC or other IV access to allow administration of 5FU via a continuous infusion pump. All agents should be administered within SOC drug administration guidelines. Appropriate dose modifications for each agent are described in Section 9.0. See drug monographs/package inserts for full details on each agent.

Agent	Dose*	Route	Schedule
Oxaliplatin	85 mg/m ² in 250 cc D5W	IV before irinotecan	Day 1,15 of each 28 day cycle

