Non-Hematologic Toxicities				
If mucositis is >Grade 2 on the day of treatment, treatment will be delayed ¹ for 1 week. Resume treatment when mucositis <Grade 2. Consider use of mouth wash/rinse.	Mucositis	Irinotecan	5FU	Oxaliplatin
	≤Grade 2	Maintain dose	Maintain dose	Maintain dose
	Grade 3	Maintain dose	↓1 dose level	Maintain dose
	Grade 4	Maintain dose	↓2 dose levels	Maintain dose

Table 4: Dose Modifications for Toxicity				
If diarrhea is \geq Grade 2, on the day of treatment, treatment will be delayed ¹ 1 week. Once diarrhea is $<$ Grade 2, proceed with dose adjusted per table.	Diarrhea	Irinotecan	5FU	Oxaliplatin
	Grade 2	↓1 dose level	Maintain dose	Maintain dose
	Grade 3	↓1 dose level	↓1 dose level	Maintain dose
	Grade 4	↓2 dose levels	↓2 dose levels	↓1 dose level
Electrolyte abnormalities, regardless of grade, do not require dose reductions or dose delays but should be corrected with aggressive supplementation.	Electrolyte Abnormalities	Irinotecan	5FU	Oxaliplatin
	Any Grade	Maintain dose. Treating physician may reduce dose for grade 3-4, if deemed appropriate		
Non-Hematologic Toxicities				
On Day 1 or Day 15	Toxicity at any point during cycle	Dose Level for Subsequent Administration		
If HFSR is $>$ Grade 2, delay ¹ treatment for 1 week. Once HFSR is \leq Grade 2, proceed with dose adjusted per table.	HFSR	Irinotecan	5FU	Oxaliplatin
	\leq Grade 2	Maintain dose	Maintain dose	Maintain dose
	Grade 3	Maintain dose	↓1 dose level	Maintain dose
	Grade 4	Maintain dose	↓2 dose levels	Maintain dose
If neuropathy Grade 2 and persisting between treatments, or \geq Grade 3, delay ¹ treatment for 1 week. Once neuropathy is \leq Grade 2 and not persisting, proceed with dose adjusted per table.	Neuropathy- motor and/or sensory	Irinotecan	5FU	Oxaliplatin
	Grade 2 and persisting between treatments, OR new onset Grade 3 resolving to \leq Grade 2 between treatments	Maintain dose	Maintain dose	↓1 dose level
	First recurrence of Grade 3 resolving to \leq Grade 2 between treatments	Maintain dose	Maintain dose	↓1 further dose level (i.e. to dose level -2)
	Second recurrence of Grade 3 resolving to \leq Grade 2 between treatments, OR Grade 3 persistent between treatments, OR any Grade 4	Maintain dose	Maintain dose	Discontinue
If bilirubin is $>$ 2mg/dL, delay ¹ treatment for 1 week. Once \leq 2mg/dL, proceed with dose adjusted per table.	Increased Bilirubin³	Irinotecan	5FU	Oxaliplatin
	$>$ 2 mg/dL	↓2 dose levels	Maintain dose	Maintain dose

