Thromboembolism: When oxaliplatin was used in combination with 5FU and leucovorin in previously untreated advanced CRC, the percent of patients who experienced thromboembolic events was 6%.

The following toxicities are noted with particular Warnings and Precautions in the prescribing information for Eloxatin®:

1. Neuropathy: Oxaliplatin is associated with two types of neuropathy:
 - a. **An acute, reversible, primarily peripheral, sensory neuropathy that is of early onset, occurring within hours or one to two days of dosing, that resolves within 14 days, and that frequently recurs with further dosing.** The symptoms may be precipitated or exacerbated by exposure to cold temperature or cold objects and they usually present as transient paresthesia, dysesthesia and hypoesthesia in the hands, feet, perioral area, or throat. Jaw spasm, abnormal tongue sensation, dysarthria, eye pain, and a feeling of chest pressure have also been observed. The acute, reversible pattern of sensory neuropathy was observed in about 56% of study patients who received oxaliplatin with 5FU/leucovorin. In any individual cycle acute neurotoxicity was observed in approximately 30% of patients. In adjuvant patients the median cycle of onset for grade 3 peripheral sensory neuropathy was 9 in the previously treated patients the median number of cycles administered on the oxaliplatin with 5FU/leucovorin combination arm was 6.

An acute syndrome of pharyngolaryngeal dysesthesia seen in 1–2% (grade 3/4) of patients previously untreated for advanced colorectal cancer, and the previously treated patients, is characterized by subjective sensations of dysphagia or dyspnea, without any laryngospasm or bronchospasm (no stridor or wheezing). Ice (mucositis prophylaxis) should be avoided during the infusion of oxaliplatin because cold temperature can exacerbate acute neurological symptoms.

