- b. **A persistent (>14 days), primarily peripheral, sensory neuropathy that is usually characterized by paresthesias, dysesthesias, hypoesthesias, but may also include deficits in proprioception that can interfere with daily activities (e.g. writing, buttoning, swallowing, and difficulty walking from impaired proprioception).** These forms of neuropathy occurred in 48% of the study patients receiving oxaliplatin with 5FU/leucovorin. Persistent neuropathy can occur without any prior acute neuropathy event. The majority of the patients (80%) who developed grade 3 persistent neuropathy progressed from prior Grade 1 or 2 events. These symptoms may improve in some patients upon discontinuation of oxaliplatin.

Overall, neuropathy was reported in patients previously untreated for advanced colorectal cancer in 82% (all grades) and 19% (grade 3/4), and in the previously treated patients in 74% (all grades) and 7% (grade 3/4) events. Information regarding reversibility of neuropathy was not available from the trial for patients who had not been previously treated for colorectal cancer.

The following warnings and precautions are less common but serious adverse events associated with oxaliplatin:

2. **Anaphylactic Reactions:** These have been reported, and may occur within minutes of oxaliplatin administration. Epinephrine, corticosteroids, and antihistamines have been employed to alleviate symptoms. Grade 3/4 hypersensitivity, including anaphylactic/anaphylactoid reactions, to oxaliplatin has been observed in 2–3% of colon cancer patients. These allergic reactions which can be fatal, can occur within minutes of administration and at any cycle, and were similar in nature and severity to those reported with other platinum-containing compounds, such as rash, urticaria, erythema, pruritus, and, rarely, bronchospasm and hypotension. The symptoms associated with hypersensitivity reactions reported in the previously untreated patients were urticaria, pruritus, flushing of the face, diarrhea associated with oxaliplatin infusion, shortness of breath, bronchospasm, diaphoresis, chest pains, hypotension, disorientation and syncope. These reactions are usually managed with standard epinephrine, corticosteroid, antihistamine therapy, and may require discontinuation of therapy. Drug-related deaths associated with platinum compounds from anaphylaxis have been reported.

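### The only planned adverse-event analysis covers grades 3 to 5 in undefined categories, so it does not meet the objective of describing adverse events and omits most neuropathy and diarrhea

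*Combined protocol and SAP*

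**What the plan says.** Secondary objective 1 (section 2.2) is "To describe the adverse events associated with FOLFIRINOX when administered preoperatively in patients with resectable pancreatic cancer". It sets no grade limit. Sections 8 and 18.2 have adverse events recorded from the first dose until at least 30 days after treatment, also without a grade limit.

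The analysis in section 14.3 is narrower: "Adverse events of grades 3, 4, 5 by the CTCAE v4.3 criteria for each category listed in section 2.1.6 will be summarized". It continues: "The proportion of patients with each category of AE will be calculated with a 95% confidence interval". Section 2 contains only 2.1 to 2.4, and 2.1 is the primary objective with no subsections, so the reference leads nowhere. Section 14 plans no any-grade table and no summary of dose reductions, delays or discontinuations. The Safety population in section 14.2 is a placeholder that leaves the definition to the protocol.

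Table 4 (section 8) uses grade 2 as an action level. Its neuropathy row opens "If neuropathy Grade 2" and, where the event persists between treatments, lists a delay and an oxaliplatin reduction. Its diarrhea row lists a delay and an irinotecan reduction from grade 2.

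**The concern.** The objective asks for a description of adverse events, and section 1.4 says the study will provide safety information as a basis for later combinations. An analysis cut at grade 3 gives only the severe part of that description. The cut matters most for events that are common but mostly below grade 3, and section 13.1 shows neuropathy and diarrhea to be of that kind. Neuropathy may be affected further by the short course. Section 13.1 says that, in adjuvant patients, "the median cycle of onset for grade 3 peripheral sensory neuropathy was 9", while this trial gives four doses.

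At stake is whether the final report can state how many patients had grade 2 events that the protocol itself treats as grounds for action, and how often treatment was changed as a result. The primary endpoint and the stopping rule are not affected.

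**Working it through.** The plan attaches no number to its safety analysis, so there is no figure to reproduce.

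**Step 1. How much lies below the cut, on the protocol's own rates.** All are from section 13.1, for oxaliplatin with 5FU/leucovorin in colorectal cancer over a longer course.

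| Event and population | Any grade | Grade 3 or higher | Below the cut | Share of affected patients omitted |
|---|---|---|---|---|
| Neuropathy, previously untreated | 82% | 19% | 63 points | 63/82 = 77% |
| Neuropathy, previously treated (median 6 cycles) | 74% | 7% | 67 points | 67/74 = 91% |
| Diarrhea, previously untreated | 56% | 12% | 44 points | 44/56 = 79% |

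**Step 2. Doses in this trial.** Section 7.1 gives two 28-day cycles: "Patients will receive FOLFIRINOX on an outpatient basis on days 1 and 15 of each cycle". That is 2 × 2 = 4 doses, which agrees with the four treatments named in section 14.2.

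**Step 3. Any-grade neuropathy over four doses.** The documents give no such rate. Section 13.1 gives acute neurotoxicity in about 30% of patients in any single cycle and acute neuropathy at some time in about 56%. I take these as the assumed range, with 48 patients treated:

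- 48 × 0.30 = 14.4, about 14 patients (exact 95% CI for 14/48: 17.0% to 44.1%)
- 48 × 0.56 = 26.9, about 27 patients (exact 95% CI for 27/48: 41.2% to 70.5%)

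**Step 4. Grade 3 or higher over four doses.** Expected count = 48 × full-course rate × share of grade 3 onsets by dose 4. The documents give only the median onset, cycle 9, which I read as one dose per cycle. The share is therefore assumed: 10% as a low case; 0.5 × 4/9 = 22% if onsets accrue linearly up to the median; 1 − 2^(−4/9) = 26.5% under a constant hazard. A median of 9 caps the share at 50%. The chance of no cases is (1 − p)^48, where p is the rate times the share.

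| Share by dose 4 | Expected at 7% | Chance of none | Expected at 19% | Chance of none |
|---|---|---|---|---|
| 10% | 0.34 | 0.71 | 0.91 | 0.40 |
| 22% | 0.75 | 0.47 | 2.03 | 0.13 |
| 26.5% | 0.89 | 0.41 | 2.42 | 0.08 |
| 50% (cap) | 1.68 | 0.18 | 4.56 | 0.01 |

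So roughly 0 to 2 patients are expected in the planned table, and at most about 5. Exact 95% CIs are 0% to 7.4% for 0/48 and 0.5% to 14.3% for 2/48. Section 13.1 also reports an acute grade 3/4 throat syndrome in 1–2% of patients (48 × 0.01 to 48 × 0.02 = 0.5 to 1 patient), so zero cannot be taken for granted.

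**The case against.** **A summary of severe events is a legitimate choice, and nothing is lost from the database.** Both parts are true. A reader might infer that the trial would report neuropathy as nearly absent. The documents do not support that: a table labelled grade 3 to 5 says nothing about lower grades, so it omits them rather than reporting them as zero. The mismatch with an objective that has no grade limit remains.

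**The second sentence in section 14.3 could cover any grade.** It refers to each category of event and does not repeat the limit. But it follows directly on the grade 3 to 5 sentence and depends on the same missing section. At best the plan is ambiguous.

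**Full-course rates do not apply to four doses.** This stands. Applying 82% and 19% to 48 patients would suggest 39 with neuropathy, about 30 of them below the cut. Those rates come from longer exposure, and the same source would put about 9 of 48 (0.19 × 48) in the planned table. Step 1 is therefore used only for the severity split, and the counts come from steps 3 and 4.

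**The acute form is described as resolving within 14 days, and surgery comes about four weeks (plus or minus two) after chemotherapy.** This also stands. A reader might infer that 14 to 27 patients reach surgery with unreported neuropathy. Much of the acute form may have resolved by then. Of the persistent form section 13.1 says "These forms of neuropathy occurred in 48% of the study patients receiving oxaliplatin with 5FU/leucovorin", but it gives no rate after four doses.

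**Other sections cover the gap.** Section 17.2 requires monthly summaries of significant toxicities and dose adjustments, so dose changes are reviewed during the trial, but that is monitoring and not a planned analysis. The two questionnaires have no item on numbness or tingling. Section 8 also leaves adjustments and holds to the treating physician's judgment, so a grade 2 event does not lead to a dose change automatically. That makes a count of the actual changes more informative.

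**Conclusion.** The point holds as a gap between objective and analysis. The one planned adverse-event analysis stops at grade 3 and uses categories that are not defined, although the objective and the recording rules have no grade limit. On the protocol's own figures, 77% to 91% of patients with neuropathy and 79% of those with diarrhea fall below the cut. For this trial, about 14 to 27 of 48 patients might have neuropathy of any grade, against roughly 0 to 2, at most about 5, at grade 3 or higher.

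These counts rest on four assumptions: that rates from oxaliplatin with 5FU/leucovorin in colorectal cancer carry over to FOLFIRINOX; that 30% to 56% is a fair any-grade range for four doses; that 10% to 26% of grade 3 onsets (at most half) fall within four doses; and that the onset figure from adjuvant patients can be combined with severity rates from advanced disease. If a cycle in the source meant two doses, grade 3 onset would come later still. The mismatch itself rests on none of these assumptions. It is a moderate point: worth correcting before analysis, with no bearing on the primary endpoint.

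**What to change.** Replace the adverse-event summary sentence in section 14.3 with:

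> In all patients who received at least one dose of study treatment, AEs will be tabulated by CTCAE v4 term and maximum grade per patient (any grade, grade ≥2, grade 3–5), with 95% CIs; neuropathy and diarrhea will be shown explicitly, and the numbers of patients with a dose reduction, delay or discontinuation of each agent will be reported.

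Delete the reference to section 2.1.6. Do not put the Table 4 categories in its place: that table has no rows for anemia, fatigue or infection, which would disappear into its unspecified group. In section 14.2, define the Safety population as all patients who received at least one dose.

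The cost is a wording change and one or two extra tables from data already collected. It needs no extra visits and alters no treatment rule.
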